4.0 Test Schedule

Tests	Days Prior to Registration		Day 8, 15, 22 (Cycles 1-3), Day 15 (Cycle 4 onwards) ¹	Every cycle, pre- treatment ¹	End of Cycle 4 ¹	End of Treatment (+/-14 days) ¹
	≤30 days	≤14 days				
Complete medical history	X					
Adverse Event monitoring		X		X ¹⁶		X
Physical exam, including weight and vital signs		X		X ¹⁶		X
Height		X				
Performance status (ECOG scale)		X		X ¹⁶		X
CBC with differential		X	X	X ¹⁶		X
Chemistry group: sodium, potassium, glucose, alkaline phosphatase; Total and Direct bilirubin; SGOT (AST); serum creatinine, calcium, magnesium		X		X ¹⁶		X
LDH, Beta ₂ -microglobulin, C-reactive protein	X					
Electrophoresis of serum and urine (SPEP/UPEP)		X		X ^{3,16}		X ³
Affected immunoglobulin ²		X		X ^{2,16}		X ²
Immunofixation serum and urine	X			X ^{4,16}		X ⁴
Immunoglobulin free light chain (MML panel)		X		X ^{5,16}		X ⁵
X-ray skeletal survey or low dose full body CT ⁶	X			X ⁶		X
Physical measurement (EMD lesion) ⁷		X		X		
CT Scan, PET/CT, or MRI for measurement of EMD lesion ⁸	X			X ⁸		
Circulating plasma cell assessment (flow cytometry or peripheral smear) ⁹		X		X ^{9,16}		
Bone marrow aspirate and biopsy, myeloma FISH, metaphase cytogenetics, plasma cell proliferation, and flow cytometry	X			X ¹⁰	X ¹⁰	X
Biopsy of extramedullary lesion ¹¹	X					
Chest x-ray	X					
Serum pregnancy test ¹²		X ¹²				
ECG, 12 lead with interpretation	X					
Register patient for POMALYST REMS™ program ¹³		X ¹³				
Patient Medication Diary (Appendix II) ¹⁴				X	X	X
Mandatory tissue block ¹¹	X					
Mandatory Research Bone marrow sample ^R	X			X ¹⁰		X
Mandatory Peripheral Blood sample ^R	X			X ¹⁵		X ¹⁵

Cycle = 28 days {FOOTNOTES CONTINUE ON NEXT PAGE}

- 1) All scheduled visits will have a window of ± 7 days unless otherwise stated.
Note: Baseline labs can be used for Cycle 1, Day 1.
 - 2) Affected immunoglobulin refers to the baseline M-protein type, that is, IgG, IgA, or IgD. Not applicable if patient “non-secretory” or if patient has no heavy chain, i.e. light chain myeloma. Affected immunoglobulin is required after baseline only if it used for disease monitoring instead of SPEP (e.g. IgA myeloma).
 - 3) Urine Electrophoresis required only if used to assess disease response.
 - 4) Immunofixation (IF) needed only in the absence of M-protein to document sCR or CR.
 - 5) Serial light chain required if it is used for disease monitoring (measurable disease at baseline)

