 - 6) Skeletal survey/low dose CT not needed at baseline or any other timepoint if PET/CT is done at that timepoint. Otherwise every 365 days (12 months) or more often if clinically indicated.
 - 7) For patients with a clinically palpable lesion.
 - 8) CT or MRI or the CT portion of the PET/CT, same modality should be used at baseline and for serial evaluation. PET/CT scans are required at baseline for all patients with EMD. Assessment of EMD lesions should be performed at end of Cycle 1 and every three cycles or more frequently if clinically indicated. For patients with only skin involvement, skin lesions should be measured with a ruler with images maintained in the medical record.
 - 9) Number of circulating cells may be measured using flow cytometry or peripheral smear as is the standard practice for the institution, but same methodology should be used at every time point. This should be repeated after Cycle 1 and every 2 cycles after that or more often if clinically indicated.
 - 10) At the end of 4 cycles and only required to document CR after that. If a bone marrow was done to confirm CR prior to end of 4 cycles, no further bone marrow examination until the end of treatment.
 - 11) In patients with extramedullary soft tissue disease.
 - 12) For women of childbearing potential only. Must be done ≤ 7 days prior to registration.
NOTE: Additional pregnancy testing is required as a condition of participation in the POMALYST REMS™ program.
 - 13) All study participants must be registered into the mandatory POMALYST REMS™ program, and be willing and able to comply with the requirements of the POMALYST REMS™ program.
 - 14) The diary must begin the day the patient starts taking the medication and must be completed per protocol and returned to the treating institution.
 - 15) At baseline, end of Cycle 4, and at end of treatment. See [Section 14.0](#).
 - 16) Mayo Rochester only: Required evaluations can be done through local facility, phone contact, or by local lab as applicable if patient is unable to return to Mayo facility and is approved by study chair.
- R Research funded (see [Section 14.0](#)). Will be charged to study and not to patient’s account.

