8.11 Instruction for initiation of a new cycle of therapy

A new cycle of treatment may begin on the scheduled Day 1 of a new cycle if:

- The ANC is $\geq 1000/\mu\text{L}$
- The platelet count is $\geq 50,000/\mu\text{L}$
- Any other non-hematologic treatment -related adverse event that may have occurred has resolved to \leq Grade 1 or baseline severity.

If these conditions are not met on Day 1 of a new cycle, the subject will be evaluated weekly and a new cycle of therapy will be held until the toxicity has resolved as described above.

If any drug dosing was halted during the previous cycle and was restarted with a one-level dose reduction without requiring an interruption for the remainder of the cycle, then that reduced dose level will be initiated on Day 1 of the new cycle.

If any drug dosing was omitted for the remainder of the previous cycle or if the new cycle is held due to known hematologic toxicity newly encountered on the scheduled Day 1, then the new cycle will be started with a one-level dose reduction. If a new cycle of therapy cannot be restarted within 4 weeks of the scheduled Day 1 due to non-resolution of drug related toxicities, the patient will be removed from protocol therapy and will go to event monitoring.

→ → Use the NCI Common Terminology Criteria for Adverse Events (CTCAE) version 4.0* unless otherwise specified ← ←

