- **FLC estimation** is currently carried out using the serum FLC assay (Freelite, The Binding Site Limited, UK). Patients with kappa/lambda FLC ratio <0.26 are defined as having monoclonal lambda FLC and those with ratios >1.65 as having a monoclonal kappa FLC. The monoclonal light chain isotype is considered the involved FLC isotype, and the opposite light chain type as the uninvolved FLC type.
- **CT, PET/CT or MRI** should be performed on all patients with EMD at baseline. This should be repeated after 1 cycle and then every three cycles or more frequently if clinically indicated. The same modality should be used for serial assessment.

- **Peripheral blood testing for circulating plasma cells** should be performed in all patients with plasma cell leukemia at baseline and after 1 cycle and every two cycles thereafter. Peripheral smear or flow cytometry may be used to evaluate circulating plasma cells, but the same modality should be used throughout the study.
- **Response terms:** The following response terms will be used to define M protein response: stringent Complete Response (sCR), complete response (CR), very good partial response (VGPR), partial response (PR), Minimal Response (MR), stable disease (SD), and progressive disease (PD). EMD or PCL response definitions/criteria are detailed below.

In addition, for each response category, there will be an “unconfirmed” response category, which will be for internal use, for the purpose of guiding decision making and test ordering. These designations will be applied at the time of the first measurement at which the quantitative aspect of the response category has been satisfied without the confirmation step having been satisfied. The designation “u” will precede the standard abbreviations, and will include usCR, uCR, uVGPR, uPR, uMR, uPD.

- **Measurable disease:** Patients who have a measurable serum or urine M-protein.
 - Serum M-protein ≥ 1 g/dl
 - Urine M-protein ≥ 200 mg/24 h
 - Serum FLC assay: Involved FLC level ≥ 10 mg/dl provided serum FLC ratio is abnormal
 - At least one plasmacytoma that has a single diameter of ≥ 2 cm.
 - Plasma cell count exceeding 500/microL or 5 percent of the peripheral blood white cells

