16.32 Secondary Outcome Analyses

- 16.321 Type of response will be differentiated as biochemical vs. extramedullary disease, as defined in Section 11.6. Biochemical response will be defined as a response by serum M-protein, urine M-protein, or serum FLC assay parameters. For biochemical response, the response rate will be estimated by the number of responders divided by the number of evaluable patients who have measurable disease by serum M-protein, urine M-protein, or serum FLC assay at baseline. Extramedullary response will be defined as a response by extramedullary plasmacytoma or plasma cell count parameters. For extramedullary response, the response rate will be estimated by the number of responders divided by the number of evaluable patients. Exact binomial confidence intervals will be calculated.
- 16.322 Progression-free survival is defined as the time from registration to the earliest date of documentation of disease progression or death due to any cause. The distribution of progression-free survival will be estimated using the method of Kaplan-Meier.
- 16.323 Adverse Events: All eligible patients that have initiated treatment will be considered evaluable for assessing adverse event rate(s). The maximum grade for each type of adverse event will be recorded for each patient, and frequency tables will be reviewed to determine patterns. Additionally, the relationship of the adverse event(s) to the study treatment will be taken into consideration.

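### Scheduled EMD scans after the first follow cycle number, so toxicity holds can widen the 84-day scan gap and, on average, delay documentation of imaging-only progression in the secondary PFS estimate

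*Combined protocol and SAP*

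**What the plan says.** Section 4.0, footnote 8, sets EMD imaging by cycle: "Assessment of EMD lesions should be performed at end of Cycle 1 and every three cycles or more frequently if clinically indicated". Section 11.1 repeats this for CT, PET/CT or MRI: "This should be repeated after 1 cycle and then every three cycles or more frequently if clinically indicated". Footnote 9 and section 11.1 set circulating plasma cell counts the same way, after Cycle 1 and then every two cycles. A cycle is nominally 28 days, and footnote 1 adds: "All scheduled visits will have a window of ± 7 days unless otherwise stated".

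Section 8.11 makes the calendar length of a cycle depend on recovery. If the Day 1 conditions are not met, "the subject will be evaluated weekly and a new cycle of therapy will be held until the toxicity has resolved". The limit for each cycle is 4 weeks. Protocol therapy ends, and event monitoring begins, in this case: "If a new cycle of therapy cannot be restarted within 4 weeks of the scheduled Day 1 due to non-resolution of drug related toxicities". No cumulative limit is stated.

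Section 16.322 defines the endpoint: "Progression-free survival is defined as the time from registration to the earliest date of documentation of disease progression or death due to any cause". The only analysis given is this: "The distribution of progression-free survival will be estimated using the method of Kaplan-Meier". The documents do not anchor scans to the calendar during a hold, and they plan no sensitivity analysis for assessment timing.

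**The concern.** Progression that shows only on imaging is dated at the scan that finds it. If toxicity stretches the cycles, the next scheduled scan comes later and so does the recorded progression date. On average the shift is in the favourable direction and grows with the amount of delay. Section 2.23 names PFS as a secondary goal, and with one arm any comparison would have to be with outside data.

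Holds are plausible on the protocol's own figures. The entry minimums in section 3.13 (ANC 1000/mm³, platelets 50,000/mm³) equal the thresholds for starting a new cycle in section 8.11. Section 1.5 reports 35% grade 3 or 4 neutropenia with pomalidomide and dexamethasone.

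The patients most exposed are those followed by EMD alone. Section 11.1 does not require an M-spike for entry, and section 12.1 has a category for extramedullary disease only. Serial M-protein or free light chain tests may not reveal progression in them.

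**Working it through.** **1. The plan's own figures.** The documents give no PFS figure. The only operating figures are for the response design in section 16.24. With 10 then 17 patients, P(promising) = Σ(x=3..10) b(10,x,p) × P(Bin(17,p) ≥ 10−x). This gives 0.0994 at p = 0.25 and 0.9036 at p = 0.50 (stated 0.10 and 0.90). P(stop at interim) = P(Bin(10,p) ≤ 2) gives 0.526 and 0.055 (stated 0.53 and 0.05). The design is reproduced, and PFS does not enter it.

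**2. Scan dates.** I read the schedule as scans at the ends of Cycles 1, 4, 7 and 10. If every new cycle is held d days, the end of cycle k falls on day 28k + d(k−1) from Cycle 1 Day 1. The gap is 3(28+d), and the approximate mean lag from progression to scan is half of that.

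| Hold per cycle | Scan days | Gap | Half-gap lag | Added lag |
|---|---|---|---|---|
| 0 | 28, 112, 196, 280 | 84 | 42 | – |
| 7 | 28, 133, 238, 343 | 105 | 52.5 | 10.5 |
| 14 | 28, 154, 280, 406 | 126 | 63 | 21 |
| 28 (limit) | 28, 196, 364, 532 | 168 | 84 | 42 |

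If scans are instead done just before the next cycle starts, the day is (28+d)k (for example 35, 140, 245, 350 with 7-day holds). The first scan then moves too, but the gaps are the same.

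**3. Partial hold frequencies.** The documents give neither hold frequency nor true PFS, so both are assumed. The simulation used 100,000 patients per setting, exponential progression times with true medians of 3, 6 and 9 months, and a fraction q of cycles held d days at random. Progression was dated at the first scheduled scan after it occurred. The half-gap approximation for the added lag is 1.5 × q × d.

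| Cycles held | Days | Simulated added mean delay | 1.5qd |
|---|---|---|---|
| 10% | 7 | 1.3 to 1.9 d | 1.05 |
| 25% | 7 | 2.3 to 4.6 d | 2.6 |
| 50% | 14 | 11.0 to 15.8 d | 10.5 |
| 100% | 7 | 10.7 to 14.3 d | 10.5 |
| 100% | 28 | 42.4 to 48.1 d | 42 |

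Simulation noise reaches a few days at the longer medians, so the upper ends are somewhat inflated; the half-gap column is the steadier guide.

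**4. Progression visible on per-cycle laboratory tests.** The same simulation with an assessment every cycle adds about 11 to 21 days at the 28-day limit and mostly under 9 days in the milder settings.

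**5. Kaplan-Meier median.** When events fall on common scan dates, the observed median is the first scan on or after the true median. A true median of 4 months is 4 × 30.4375 = 121.75 days. The observed medians are then 196 days with no holds and 133, 154 and 196 days with holds of 7, 14 and 28 days in every cycle. A true median of 6 months is 182.6 days, and the observed medians are 196, 238, 280 and 196 days. The median can fall, rise or stay the same.

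**6. Circulating plasma cells.** The gap is 2(28+d): 56 days with no holds, 70 with 7-day holds and 112 at the limit.

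**The case against.** A reader might infer that holds push back every progression assessment. The documents do not support that. Table 11.5 lets any one of several non-imaging criteria define progression, including calcium, hemoglobin and creatinine. Section 4.0 schedules blood tests and measurement of palpable lesions every cycle. Unscheduled scans are allowed, held patients are evaluated weekly, and death is an event in its own right. Read as end-of-cycle, the first scan need not move, because section 8.11 holds the start of the next cycle.

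A reader might also infer that reported PFS must lengthen. The mean time to imaging-detected progression does, but step 5 shows that the median need not.

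The 168-day gap might be taken as typical. It needs a maximum hold in every cycle. Much mid-cycle toxicity leads to omitted doses that are not made up, which does not lengthen the cycle, and a hold for new hematologic toxicity brings a dose reduction. Patients whose toxicity outlasts 4 weeks leave therapy for event monitoring every 3 months, which runs on the calendar. It is therefore too strong to say that the worst-tolerating patients always gain the most.

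Finally, PFS has no hypothesis, comparator or threshold, and the plan specifies no external comparison.

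All of this limits the size and reach of the point. It does not remove the mechanism. The content of the weekly evaluation is not specified, extra scans are discretionary, and neither reliably covers silent growth in a patient followed only by EMD imaging.

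**Conclusion.** The point holds in limited form. Scheduled on-treatment EMD scans after the first depend on toxicity, and the planned gap of 84 days can reach 105 days with weekly holds in every cycle and 168 days at the formal limit. For progression seen only on those scans, the average delay runs from a few days under occasional short holds to about a month and a half at a limit that should be read as a bound. These sizes rest on assumed hold frequencies, exponential progression times and detection by scheduled scan alone. Progression found by other routes is affected less or not at all.

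The consequence is confined to the descriptive secondary PFS estimate and any outside comparison made with it. The response-rate decision rule, the 27 evaluable patients, the significance level and the power are unaffected. This is a cheap improvement rather than a flaw that threatens the trial's main conclusion.

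**What to change.** In footnote 8 and the matching bullet in section 11.1, schedule EMD imaging at Week 4 and every 12 weeks thereafter, counted from Cycle 1 Day 1 regardless of dose holds. In footnote 9 and its matching bullet, schedule circulating plasma cell assessment at Week 4 and every 8 weeks on the same clock. Keep the existing allowance for additional assessments when clinically indicated. Scans would then be due on days 28, 112, 196 and 280 whatever the holds, with a mean lag of about 42 days.

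The cost is amendment wording. The scan frequency is that already planned for an undelayed patient, though some assessments will fall mid-cycle. For patients already past these visits, add an interval-censored or assessment-timing sensitivity analysis of PFS, which requires no change to visits.

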4.2 Event Monitoring/Survival Follow-up

	Event Monitoring Phase ¹				
	q. 3 months until PD	At PD	After PD q. 6 months	Death	New Primary
Event Monitoring	X	X	X	X	At each occurrence

1. If a patient is still alive 3 years after registration, no further follow-up is required.

5.0 Grouping Factor: None**6.0 Registration Procedures****6.1 Registration Procedures-All Sites****6.11 Mayo Clinic sites:**

To register a patient, access the Mayo Clinic Cancer Center (MCCC) web page and enter the registration/randomization application. The registration/randomization application is available 24 hours a day, 7 days a week. Back up and/or system support contact information is available on the Web site. If unable to access the Web site, call the MCCC Registration Office at [REDACTED] between the hours of 8 a.m. and 4:30 p.m. Central Time (Monday through Friday).

The instructions for the registration/randomization application are available on the MCCC web page (<http://ccswww.mayo.edu/training/>) and detail the process for completing and confirming patient registration. Prior to initiation of protocol treatment, this process must be completed in its entirety and a MCCC subject ID number must be available as noted in the instructions. It is the responsibility of the individual registering the patient to confirm the process has been successfully completed prior to release of the study agent. Patient registration via the registration/randomization application can be confirmed in any of the following ways:

- Contact the MCCC Registration Office [REDACTED]. If the patient was fully registered, the MCCC Registration Office staff can access the information from the centralized database and confirm the registration.
- Refer to “Instructions for Remote Registration” in section “Finding/Displaying Information about A Registered Subject.”

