10.6 Required routine reporting

Adverse events to be graded at each evaluation and pretreatment symptoms/conditions to be evaluated at baseline per the CTCAE v4.0 grading unless otherwise stated in the table below:

SYSTEM ORGAN CLASS	Adverse event/Symptoms	Baseline	Each evaluation
Investigations	Creatinine increased	X	X
	Neutrophil count decreased	X	X
	Platelet count decreased	X	X
General disorders and administration site conditions	Fatigue	X	X
Gastrointestinal Disorders	Nausea	X	X
	Vomiting	X	X
	# of Stools	X	
	Diarrhea		X
	Constipation		X
Infections and infestations	Sepsis	X	X
Blood and lymphatic system disorders	Febrile neutropenia	X	X
Skin and subcutaneous tissue disorders	Rash, maculopapular	X	X
Nervous system disorders	Peripheral sensory neuropathy	X	X
	Peripheral motor neuropathy	X	X

10.62 Submit via appropriate MCCC Case Report Forms (i.e., paper or electronic, as applicable) the following AEs experienced by a patient and not specified in Section 10.5:

10.621 Grade 2 AEs deemed *possibly, probably, or definitely* related to the study treatment or procedure.

10.622 Grade 3 and 4 AEs regardless of attribution to the study treatment or procedure.

10.623 Grade 5 AEs (Deaths)

- Any death within 30 days of the patient's last study treatment or procedure regardless of attribution to the study treatment or procedure.
- Any death more than 30 days after the patient's last study treatment or procedure that is felt to be at least possibly treatment related must also be submitted as a Grade 5 AE, with a CTCAE type and attribution assigned.

10.63 Refer to the instructions in the Forms Packet (or electronic data entry screens, as applicable) regarding the submission of late occurring AEs following completion of the Active Monitoring Phase (i.e., compliance with Test Schedule in Section 4.0).

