^a All response categories require two consecutive assessments made at anytime before the institution of any new therapy; complete and PR, MR and SD categories also require no known evidence of progressive or new bone lesions if radiographic studies were performed. Radiographic studies are not required to satisfy these response requirements. Bone marrow assessments need not be confirmed. Each category, except for stable disease, will have a working subcategory of “unconfirmed” [prefix ‘u’] to designate first time point at which response category MAY have been achieved if confirmed.

^b Presence/absence of clonal cells is based upon the k/λ ratio. An abnormal k/λ ratio by immunohistochemistry and/or immunofluorescence requires a minimum of 100 plasma cells for analysis. An abnormal ratio reflecting presence of an abnormal clone is k/λ of $>4:1$ or $<1:2$.

^c Positive immunofixation alone in a patient previously classified as CR will not be considered progression.

^d Progressive disease should be confirmed. However, treatment may be discontinued for progressive disease that is unconfirmed per physician discretion. In this case, an objective status of PD should be entered on the measurement form and progressive disease should be reported on the event monitoring form.

^e Does not apply to EMD or PCL

^f In the case where a value is felt to be a spurious result per physician discretion (for example, a possible lab error), that value will not be considered when determining the lowest value.

11.6 Types of Response:

11.61 Biochemical response will be defined as detailed above for serum, urine, and FLC.

11.62 Extramedullary disease response will be defined as detailed above for plasmacytomas and plasma cell leukemia.

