13.0 Treatment/Follow-up Decision at Evaluation of Patient

13.1 Patients who are sCR, CR, VGPR, PR, or SD (or usCR, uCR, uVGPR, uPR) will continue treatment per protocol.

13.2 Patients who develop progressive disease while receiving therapy will go to the event-monitoring phase.

13.3 Patients who go off protocol treatment for reasons other than PD will go to the event-monitoring phase per Section 18.0.

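### After a stop without progression no disease assessment is required, yet PFS runs on to documented progression with no censoring rule, so PFS may be overstated for these patients

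*Combined protocol and SAP*

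**What the plan says.** On treatment, Section 4.0 and its footnotes set the assessments. M-protein is read each cycle. Circulating plasma cells are counted after Cycle 1 and then every two cycles. For lesions, footnote 8 says: "Assessment of EMD lesions should be performed at end of Cycle 1 and every three cycles or more frequently if clinically indicated". The row for "CT Scan, PET/CT, or MRI for measurement of EMD lesion" has no entry in the End of Treatment column, and neither has the circulating plasma cell row. Section 10.63 equates the Active Monitoring Phase with compliance with this schedule.

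Section 13.3 covers those who stop early: "Patients who go off protocol treatment for reasons other than PD will go to the event-monitoring phase per Section 18.0". Section 18.2 refers back to Section 4.2, whose table has a single row, event monitoring, with the pre-progression interval given as "q. 3 months until PD". No test is listed. Follow-up ends 3 years after registration for patients still alive.

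Section 16.322 defines the endpoint: "Progression-free survival is defined as the time from registration to the earliest date of documentation of disease progression or death due to any cause". It adds: "The distribution of progression-free survival will be estimated using the method of Kaplan-Meier". It says nothing about patients who stop without PD, missed assessments or new therapy.

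**The concern.** PFS here is dated by documentation, so it depends on how closely disease is watched. A patient on treatment has scheduled assessments. A patient who stopped for toxicity, refusal or the investigator's decision has a scheduled contact but no scheduled assessment. If both stay at risk on one Kaplan-Meier curve, a progression that nobody looked for counts as progression-free time until it comes to light.

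Such stops are foreseeable. Section 8.0 sends patients to event monitoring when both ixazomib and pomalidomide are discontinued, Section 8.11 when a new cycle cannot start within 4 weeks, and Section 13.4 lists further reasons. At stake is the accuracy of a named secondary goal (Section 2.23): the more patients stop without PD, the more of the curve rests on time in which no assessment was required.

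**Working it through.** The plan gives no PFS median, event count or power, so there is no PFS figure to reproduce. Its response design does reproduce. With 10 then 27 patients, stopping at 2 or fewer responders and succeeding at 10 or more, exact binomial calculation gives alpha 0.0994 (stated 0.10) and power 0.9036 (stated 0.90). That rule contains no PFS term.

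**Required assessment before and after a stop**
- Before: cycles last 28 days, so lesions are imaged at day 28 and then every 3 × 28 = 84 days. Plasma cell leukemia is followed by blood every 2 × 28 = 56 days after Cycle 1.
- After: one contact about every 91 days, with no test named.

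**Size at 12 months, under assumptions**

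Assumed, because the documents give none of these: exponential time to progression with true median m = 4, 6 or 8 months; a share f = 20%, 30% or 40% stopping before progression, independently of it; and an exponential detection lag after an unscanned progression, with mean L = 3 or 6 months. Biochemical detection and deaths before detection are left out; both would shorten the lag and reduce the effect.

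Let λ = ln 2/m, σ = λf/(1 − f) and μ = 1/L. A scheduled scan falls at day 28 + 4 × 84 = 364, almost exactly 12 months, so with scanning continued PFS at 12 months is close to exp(−12λ). The overstatement is the share of patients who stop before progression, progress before month 12 and are still undetected at month 12:

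G = ∫₀¹² λe^(−λp) (1 − e^(−σp)) e^(−μ(12−p)) dp = λe^(−12μ)(A − B),

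with A = (1 − e^(−12a))/a, a = λ − μ, and B = (1 − e^(−12b))/b, b = λ + σ − μ.

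- Smallest case (m = 8, f = 20%, L = 3): λ = 0.08664, σ = 0.02166, μ = 0.33333; A = 74.20, B = 61.70; G = 0.001587 × 12.49 = 0.020. PFS goes from 35.4% to 37.3%.
- Largest case (m = 4, f = 40%, L = 6): λ = 0.17329, σ = 0.11552, μ = 0.16667; A = 11.536, B = 6.297; G = 0.023452 × 5.239 = 0.123. PFS goes from 12.5% to 24.8%.

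Gain in percentage points (L = 3 / L = 6):

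| True median | 12-month PFS, scanned | f = 20% | f = 30% | f = 40% |
|---|---|---|---|---|
| 4 months | 12.5% | 3.2 / 5.9 | 4.9 / 9.0 | 6.5 / 12.3 |
| 6 months | 25.0% | 2.6 / 4.4 | 4.1 / 7.0 | 5.7 / 9.8 |
| 8 months | 35.4% | 2.0 / 3.2 | 3.2 / 5.2 | 4.5 / 7.5 |

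Simulation under the same assumptions agrees with this range.

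**Why the median is a poor gauge.** Scans fall at 0.9, 3.7, 6.4, 9.2 and 12.0 months, so the observed median sits on a step. In simulation it did not move at all for true medians of 4, 5 or 7 months.

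**Dependence on the handling of stops.** A separate simulation included deaths, with a true median of 6 months and 20% stopping. The 3-year restricted mean was 9.9 months with scanning continued. It was 10.1 or 10.7 with no scans and a median lag of 2 or 6 months, and 9.9 with censoring at the stop when stopping is independent of progression.

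**The case against.** The strongest reply is that monitoring does not end. The contact continues every 3 months until PD, Table 11.5 (note d) provides that "progressive disease should be reported on the event monitoring form", and Section 18.5 asks for supporting documents for progression after study therapy. The Case Report Form packet, which is not among the documents, may ask for more. Progression can also be called on M-protein, free light chains, plasma cells, calcium, hemoglobin or creatinine, and death is an event. Since Section 16.322 is silent, the analyst could censor at the stop.

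Much of this stands. A reader might infer that assessment ceases altogether; the documents show only that none is required, and sites may continue to test. A reader might also infer that PFS must lengthen. It does so only if unassessed time is credited as event-free and detection is in fact late. Finally, a simulation with a true median of 6 months and 30-40% stopping moves the observed median from about 6.4 to 7.2-9.2 months. That is not a fair headline: 6 months lies just before the 6.4-month scan, where a small delay tips the median toward the next step.

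What does not stand is that the contact closes the gap. A form records a progression that someone has found. Section 11.1 requires no M-spike for entry and Section 12.1 allows for patients with extramedullary disease only, for whom lesion measurement is the main route to PD. The post-therapy documents named in Section 18.5 include no CT, PET/CT, MRI or plasma cell count. Leaving censoring to the analyst is not a rule either.

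**Conclusion.** The point holds in a limited form. After a stop without PD the plan requires no disease assessment, and Section 16.322, read as written, keeps the patient at risk until documented progression or death. PFS may therefore be overstated for these patients. Patients who stop because of PD already have their event and are not affected.

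The overstatement is about 2-12 percentage points at 12 months, conditional on 20-40% non-PD stops, mean lags of 3-6 months, true medians of 4-8 months and independent stopping. These are assumptions; the documents support no single figure.

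A reader might go on to infer that the trial's conclusion would favor a poorly tolerated regimen. The documents do not support that: PFS is a descriptive secondary estimate in a single-arm trial, with no hypothesis or comparator, and the go/no-go rule uses confirmed response alone. The change is still worth making, because without recorded assessment dates the bias cannot be bounded afterwards.

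**What to change.** In Section 4.2, for patients off treatment without PD, record at each existing 3-month contact, until PD or new therapy, the date and result of the last disease assessment performed: lesion measurement, plasma cell count, and M-protein or free light chains as applicable. No new scan is mandated. This matters because Section 3.19a asks patients to return only during the Active Monitoring Phase.

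In Section 16.322, keep the planned analysis and add a sensitivity Kaplan-Meier curve that censors patients who stop without PD at their last adequate disease assessment. Define adequate in advance, for example as an assessment of the parameter followed for that patient under Sections 12.1 and 12.2. Show both curves together and report how many patients stopped before PD.

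The cost is a few lines of text, slightly more data entry and one extra curve. The censored curve has its own weakness: if patients who stop differ in prognosis, the censoring is informative and the bias can go either way. It should therefore stand beside the planned curve and not replace it.
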